### 5.1 Subject Inclusion Criteria

Subjects must meet all of the inclusion criteria to be enrolled in this study.

1. Clinician suspected LRTI based on the presence of at least two qualifying symptoms OR one qualifying symptom and at least one qualifying vital sign.

 LRTI will include acute bronchitis, tracheitis, tracheobronchitis, asthma exacerbation, and acute exacerbation of COPD but does not include known pneumonia.

 New cough, worsening of chronic cough, new sputum production, increased volume or purulence of chronic sputum production, chest pain, and difficulty breathing

 Fever (Provider or patient-measured temperature  $\geq 37.8^{\circ}\text{C}$  ( $100.0^{\circ}\text{F}$ ) or patient-reported feverishness), tachycardia of  $\geq 90$  beats/minute, tachypnea of  $>20$  breaths/minute

2. Males and females age  $\geq 18$  years old.
3. Presentation  $\geq 24$  hours and  $\leq 28$  days after the onset of at least one qualifying symptom related to the acute episode of illness.
4. Ability to understand study procedures and willing and able to comply with all required procedures and visits for the entire length of study.
5. Provide written informed consent before initiation of any study procedures.

## 5.2 Subject Exclusion Criteria

All subjects meeting any of the exclusion criteria at baseline will be excluded from study participation.

1. Hospitalized prior to screening and enrollment. Subjects enrolled in clinic or ED setting and then hospitalized during the same clinical encounter may be included.
2. Chronic pulmonary conditions at the investigator's discretion

 Such as:

- Noninvasive ventilation use for any indication other than obstructive sleep apnea
- Long-term invasive mechanical ventilation for any indication
- Known diagnosis of cystic fibrosis or chronic bronchiectasis.

3. Receipt of an investigational product within 30 days prior to Day 1 or plans to potentially start any investigational product within 30 days after the subject's anticipated study completion.
4. Current enrollment in another clinical trial of an investigational agent
5. Known or suspected infection at any other anatomic site requiring antibacterial therapy.
6. Immunosuppression.

 Includes:

- HIV infection with  $\text{CD4} < 200$  based on last known measurement or patient-reported value
- History of hematologic malignancies

- *Receipt of chemotherapy within the previous 6 months or anticipated receipt of chemotherapy during the study period (1 month)*
  - *Known to have an absolute neutrophil count of <500 cells/mL or an expectation of an absolute neutrophil count of <500 cells/mL during course of the study,*
  - *Current systemic corticosteroid use (equivalent of 20mg prednisone per day for  $\geq 2$  weeks within the last month)*
  - *Systemic non-steroid immunosuppressive or biologic therapy for transplant, rheumatologic conditions, or other conditions within the last month. Biologics used specifically for control of moderate to severe asthma, including anti-IgE monoclonal antibody therapy (Xolair) or IL-5 monoclonal antibodies (Mepolizumab and Reslizumab) are allowed.*
7. Contraindication to the use of azithromycin including history of allergy or intolerance to azithromycin or known prolonged QTc interval (>500msec).
  8. Any condition that in the judgment of the referring provider or site investigator precludes participation because it could affect subject safety or ability of subject to participate in this trial.
  9. Prior use of azithromycin in the past two weeks.
  10. Use of any systemic antibiotic in the previous 24 hours.
  11. Previous randomization in this trial.

### **5.3 Subject Randomization Criteria**

Once enrolled, to be eligible for randomization subjects also must have PCT  $\leq 0.25$  ng/mL.

## **5.4 Treatment Assignment Procedures**

### **5.4.1 Randomization Procedures**

Per International Council on Harmonisation (ICH) guideline E6: Good Clinical Practice (GCP), screening records will be kept at each participating site to document the reason why an individual was screened, but failed trial entry criteria. The reasons why individuals failed screening will be recorded on screening logs maintained by each site. Once consented and upon entry of demographic data and confirmation of eligibility for this trial, the subject will be enrolled. Only if the PCT is confirmed to be  $\leq 0.25$  ng/mL, will the subject be randomly assigned to 1 of 2 groups (1:1 ratio) to receive either azithromycin or placebo. Subjects with a PCT  $> 0.25$  ng/mL will remain enrolled but will not be randomized to receive study drug.

Enrollment of subjects will be performed online using AdvantageEDC. Lists of randomized treatment assignments will be prepared by statisticians at The Emmes Corporation and included

in The Emmes Corporation's Internet Data Entry System (IDES). IDES will assign each randomized subject a treatment code from the list after the necessary data has been entered into the system. Each site will have a supply of bottles pre-labeled with treatment numbers. Once a participant is assigned a treatment number, the corresponding bottle will be distributed to the participant. An unblinded pharmacist at each site will be provided with a treatment key, which links the treatment code to the actual treatment assignment, which will be kept in a secure place. Subjects will be stratified by site.

Instructions for subject enrollment are included in the Manual of Procedures (MOP). Manual back-up randomization procedures are provided in the MOP for use in the event that the site temporarily loses access to the Internet or the online enrollment system is unavailable.

### **5.4.2 Masking Procedures**

This is a double-blind clinical trial with respect to treatment arm. Subjects, investigators, study personnel performing any study-related assessments following randomization, and laboratory personnel performing assays will be blinded to treatment group assignment.

The study product and placebo will be dispensed by the site Research Pharmacist. The study product will be labeled with a numerical code that ensures site investigators, site staff, and subjects remain blinded to the treatment assignment. For subjects randomized to placebo, the placebo will resemble the appearance of the active study product. All study products will be packaged with an identical appearance. The site Research Pharmacist will be blinded to the treatment assignment at the time product is dispensed but may be unblinded to an individual subject's treatment assignment, if clinically indicated as determined by the treating clinician and the study's site investigator.

### **5.4.3 Reasons for Withdrawal and Discontinuation of Treatment**

#### **Subject Withdrawal**

Subjects may voluntarily withdraw their consent for study participation at any time and for any reason, without penalty.

A subject may withdraw or be withdrawn from the study for any of the following reasons:

- Withdrawal of consent
- Subject lost to follow-up
- Termination of the study
- As deemed necessary by the site principal investigator or appropriate sub-investigator for noncompliance or other reasons
- Any new information becomes available that makes further participation unsafe.

Subjects who wish to withdraw from further study participation will be asked to continue to participate in follow-up visits. At the time of withdrawal, subjects will undergo an early termination visit, if they are not willing to participate in the remaining follow-up visits.

If a subject experiences any individual halting rule, as defined in Section 9.5.2, they will discontinue treatment with the study drug but will not be withdrawn from the study.

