#### **5.4.4 Handling of Withdrawals and Discontinuation of Treatment**

The primary reason for withdrawal from the study will be recorded on the Study Status data collection form. Subjects will be encouraged to complete an Early Termination Visit. Although subjects are free to withdraw at any time or may be withdrawn by the site principal investigator or appropriate sub-investigator at any time, subjects who receive at least one dose of study product will be encouraged to remain in the study for follow-up safety assessments.

Every attempt will be made to follow all protocol defined safety follow-up (solicited adverse events) to resolution or stabilization.

Subjects who withdraw, or are withdrawn or terminated from the study, or discontinue treatment will not be replaced.

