## 7.3 Follow-up Visits for Randomized Subjects

### 7.3.1 Visit 2 (Day 3 + 1 day)

Study subjects will be evaluated on Day 3 via telephone. During the telephone call, study personnel will assess LRTI signs and symptoms. If the study team identifies concerns about worsening of clinical status, the subject will be advised to seek care from his/her provider or the nearest ER if indicated. Study staff will assist in facilitating the follow up appointment. This includes signs or symptoms of pneumonia (including fever, increased difficulty breathing, or increased/worsening cough) or development of a severe solicited event. The study staff will also review any new or changed concomitant medications with the subject. UADEs will be recorded if any occur.

Study staff will also ask about medication compliance and any solicited adverse events.

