### **7.3.5 Early Termination Visit**

Subjects who are withdrawn from the study will be asked to complete an early termination visit. Procedures at the early termination visit will be identical to the next scheduled visit for outcome assessment. Subjects who withdraw from the study will be asked if they agree to receive a follow-up phone call approximately one week after their withdrawal, which will constitute the early termination visit. If the subject agrees, study staff will determine if any follow-up medical care was sought, any solicited adverse events occurred or if there was any change in medical history.

If the subject presents to the Early Termination visit with symptoms concerning for active illness in need of medical attention, such as fever and/or elevated respiratory rate, the study team will refer the subject to seek care and to follow up with their primary care provider.

UADEs will be recorded if any occur.

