### 9.5.2 Individual Halting Rules (Termination of Study Product Administration)

Study product administration may be discontinued if any of the following criteria are met:

- Any clinical adverse event (AE), intercurrent illness, or other medical condition occurs that, in the opinion of the investigator, continued receipt of study product would not be in the best interest of the subject;
- New onset of illness or condition that meets exclusion criteria, at the investigator's discretion
- Inadequate clinical response that requires off-study antimicrobial therapy.
  - Subjects who require off-study antimicrobial therapy will be defined as having an inadequate clinical response.

Subjects may stop study drug treatment at any time of their own volition or at the advice of their treating provider or the study investigators. Subjects who stop study product for any reason will be regarded as having withdrawn from treatment but not as having withdrawn from the study (i.e, subjects will be asked to continue to participate in follow-up visits). All subjects with an inadequate clinical response will be referred to a non-study healthcare provider for evaluation and possible treatment outside of the clinical study. If requested, unblinding can occur if clinically indicated as determined by the treating clinician and the study's site investigator.

At the time of withdrawal, subjects will undergo an early termination visit if they are not willing to participate in the remaining follow-up visits.

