## **11.4 Final Analysis Plan**

The intention-to-treat (ITT) analysis population will consist of all randomized subjects. According-to-protocol (ATP) analysis populations will consist of subjects with no major protocol deviations regarding inclusion/exclusion criteria that consumed 5 doses of study product by Visit 3. The first dose of study drug should be taken within 24 hours of randomization. Subjects who miss a scheduled dose but resume the recommended dosing schedule within 24 hours remain eligible for ATP. However, in order for a subject to be eligible for the ATP-5 analysis, Visit 3 should be performed on or after the last day of study drug consumption while remaining within the 5+3 window. The ATP-5 analysis population will have the further restriction that the subjects must have completed an in-person Visit 3 within the protocol-defined time window. The ATP-11 analysis population will consist of the ATP analysis population with the further restriction that the subjects must have completed Visit 4 within the protocol-defined time window. The ATP-28

analysis population will consist of the ATP analysis population with the further restriction that the subjects must have completed Visit 5 within the protocol-defined time window.

Unless otherwise stated, all hypothesis tests and confidence intervals will be two-sided with  $\alpha=0.05$ . Statistical tests and confidence intervals will not correct for multiplicity.

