7. STUDY SUBJECTS

7.1. Disposition of Subjects

Reasons for screening failures will be summarized in [Table 12](#). The completion status and reasons for early termination or treatment discontinuation will be summarized ([Table 8](#) and [Listing 2](#)). A subject could be discontinued early due to an AE (serious or non-serious), loss to follow-up, non-compliance with study, voluntary withdrawal, withdrawal at the investigator request, termination of the site by the sponsor, termination of the study by the sponsor, death, lack of eligibility at enrollment, inadequate clinical response, or becoming ineligible after enrollment.

Subject disposition and eligibility for analysis will be summarized in a CONSORT flow diagram ([Figure 1](#)).

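### Investigator withdrawal from the study for noncompliance permits avoidable, adherence-related missing Day 5 outcomes and is hard to reconcile with Protocol 9.5.2

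*Protocol*

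**What the plan says.** Protocol 5.4.3 lists the reasons for which a subject may leave or be removed from the study, not merely from study drug. One of them is "As deemed necessary by the site principal investigator or appropriate sub-investigator for noncompliance or other reasons". SAP 4.3.3 carries the same list. Protocol 5.4.4 sets no time limit: subjects "may be withdrawn by the site principal investigator or appropriate sub-investigator at any time". SAP 7.1 includes among its reasons for early discontinuation "loss to follow-up, non-compliance with study, voluntary withdrawal, withdrawal at the investigator request".

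Protocol 9.5.2 takes a different line for dosing: "Subjects who stop study product for any reason will be regarded as having withdrawn from treatment but not as having withdrawn from the study". The closing paragraph of 5.4.3 likewise keeps subjects who meet an individual halting rule in the study.

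On the analysis side, Protocol 11.4 states: "The intention-to-treat (ITT) analysis population will consist of all randomized subjects". Under SAP 6.3.1 and 8.4.1 a missing Day 5 outcome is multiply imputed under missing at random. SAP 3.3.1 treats an out-of-window visit as missing in the ITT analysis.

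**The concern.** An ITT analysis needs the Day 5 outcome of non-adherent subjects as much as anyone's. A rule that lets the site end their participation can turn an obtainable outcome into a missing one, for a reason connected with adherence.

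Adherence may be related both to response and to arm, for example through lack of effect on placebo or intolerance on azithromycin. The imputation model in SAP 8.4.1 uses treatment group, site, age, gender, visit day and fever. It has no term for adherence or reason for withdrawal. Its donors are ATP-5 subjects, who by definition took five doses. A subject withdrawn for noncompliance is therefore imputed as if adherent. In a non-inferiority trial, if poorly responding placebo subjects are the ones lost, that error favours the conclusion sought.

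**Working it through.** **When the outcome is lost.** Two conditions must both hold.

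1. Withdrawal precedes Visit 3. The only earlier scheduled compliance check is the Day 3 (+1) telephone call: "Study staff will also ask about medication compliance and any solicited adverse events". The main check, memory aid and container, takes place at Visit 3 itself (Protocol 6.5).
2. No usable assessment falls in the Day 5 to Day 8 window. Protocol 7.3.5 asks withdrawn subjects for an early termination visit: "Procedures at the early termination visit will be identical to the next scheduled visit for outcome assessment". It also allows a "follow-up phone call approximately one week after their withdrawal, which will constitute the early termination visit". After withdrawal on Day 3 or 4, a call one week later falls on about Day 10 or 11. That is outside the window, and a call supplies no in-person vital signs, which the primary endpoint uses.

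**Plan figures used.** Margin 12.5 points, 57.6% improvement, two-sided 95% interval, 674 randomised (337 per arm), 16.9% planned loss. The loss step reproduces: 560 / (1 − 0.169) = 673.9, rounded up to 674. From the stated inputs I get 262 per arm with continuity correction (524 in total), so 560 is on the conservative side. Nothing below rests on it. The plan gives no rate of withdrawal for noncompliance, so every rate below is an assumption.

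**Placebo-only scenario, at the non-inferiority boundary.** True rates are 57.6% on azithromycin and 57.6 − 12.5 = 45.1% on placebo. A fraction w of placebo subjects is withdrawn, with an assumed true success rate of 30%. Because treatment group is in the imputation model, they are imputed near the placebo completers' rate:

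- completers' rate c = (45.1 − 30w) / (1 − w); bias = c − 45.1
- SE = √[(0.576 × 0.424 + 0.451 × 0.549) / 337] = 0.0382
- type I error = Φ(bias / SE − 1.96)

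| w | c | Bias (points) | Type I error |
|---|---|---|---|
| 3% | 44.2 / 0.97 = 45.57% | 0.47 | Φ(0.122 − 1.96) = 3.3% |
| 5% | 43.6 / 0.95 = 45.89% | 0.79 | Φ(0.208 − 1.96) = 4.0% |

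**Same assumption on azithromycin only.** At w = 3%, completers run at (57.6 − 0.9) / 0.97 = 58.45%. The bias is 0.85 points against placebo, and type I error falls to Φ(−0.223 − 1.96) = 1.5%.

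**Loss in both arms.** Let a fraction f be missing per arm, with true placebo-minus-azithromycin difference D among the missing. Completers then differ by d = (−12.5 − fD) / (1 − f), with 337(1 − f) per arm, and type I error = Φ((d + 12.5) / SE − 1.96), with the SE recomputed for the completers.

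| f (assumed) | D = −30 points | D = 0 |
|---|---|---|
| 2% | 3.1% | 2.1% |
| 5% | 4.2% | 1.7% |
| 10% | 7.0% | 1.1% |
| 16.9% | 13.3% | 0.5% |

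The last row is a ceiling, because 16.9% covers every loss from ATP-5.

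**Can the tipping-point grid show it?** With 57.6% observed in both arms and imputed alike, the lower bound is −7.5%. With all missing azithromycin subjects counted as successes and all missing placebo subjects as failures, it is −9.5% at f = 2%, −12.5% at 5% and −17.5% at 10%. To reach −12.5%, the missing subjects in the two arms must differ by about 100 points at 5%, 50 at 10% and 30 at 16.9%.

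**The case against.** The case on the other side is substantial.

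- *The text is a permission, not a rule.* For missed doses, Protocol 6.5 prescribes documentation and counselling, and 11.4 makes incomplete dosing a matter of ATP membership. A reader might infer that non-adherent subjects as a class lose their Day 5 outcome. The documents do not say so.
- *The sections may not contradict each other outright.* Protocol 9.5.2 concerns study product. The 5.4.3 ground does not name study product, and SAP 7.1 speaks of compliance with the study, so it could mean missed visits or procedures. That stands as a reading, but nothing in 5.4.3 confines the ground to it. A subject who misses doses can still be handled in two ways.
- *Follow-up is sought.* An early termination visit is requested, and SAP 6.5 intends it to record components of clinical improvement. This narrows the gap without closing it. In 5.4.3 the request to continue visits is addressed to subjects who wish to withdraw, and 5.4.4 encourages staying for safety follow-up.
- *A tipping-point analysis is planned.* SAP 8.2.4 and Table 27 vary imputed success from 0% to 100% in each arm, which covers the adverse scenario. SAP 8.1.1, however, rests the conclusion on the primary analysis alone.
- *The size could be overstated.* A reader might impute withdrawn placebo subjects at 57.6%, giving 0.83 and 1.38 points and type I error of 4.1% and 5.5%. At the boundary that is the azithromycin rate. With treatment group in the model, the smaller figures apply.

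**Conclusion.** The point holds as a permitted and avoidable source of adherence-related missing Day 5 data, which the imputation model cannot represent. Under the stated assumptions (3% or 5% placebo-only withdrawal, 30% success among those withdrawn), type I error rises from 2.5% to about 3.3% or 4.0%. Neither the rates nor the 30% come from the documents. Withdrawal concentrated on azithromycin, or no difference between arms among the missing, moves the error below 2.5%. The effect is large only if the loss is large and the missing subjects differ strongly between arms.

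A reader might conclude that the ITT analysis is undermined or becomes a per-protocol analysis. That is not shown: no frequency is given, loss of the outcome needs both conditions above, and the direction is not fixed. The change is still worth making because it costs almost nothing.

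A related point decides whether the change would work. Read literally, the pseudo-code in SAP 8.4.1 builds each completed dataset from ATP-5 data plus imputed rows. A non-adherent subject's observed Day 5 result could then be left out or replaced, despite the ITT definition.

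**What to change.** 1. Reconcile Protocol 5.4.3 and 5.4.4, and SAP 4.3.3 and 7.1, with Protocol 9.5.2 by removing noncompliance as a ground for investigator withdrawal from the study.
2. State that noncompliance with study product or visits affects ATP membership only, and that Visits 3 to 5 are still attempted for every randomised subject who has not withdrawn consent.
3. Leave the investigator's discretion on safety and all study-drug decisions as they are. Removing the whole phrase, including its general second limb, would go further than this point requires.
4. In SAP 8.4.1, state that observed Day 5 outcomes of subjects outside ATP-5 are kept in the completed ITT datasets, and correct the pseudo-code to match.

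The cost is wording in two protocol sections and two SAP sections, plus a clarification of the imputation code. No visits are added, since Visits 3 to 5 are already scheduled for every randomised subject, and the sample size stays at 674.

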#### **5.4.4 Handling of Withdrawals and Discontinuation of Treatment**

The primary reason for withdrawal from the study will be recorded on the Study Status data collection form. Subjects will be encouraged to complete an Early Termination Visit. Although subjects are free to withdraw at any time or may be withdrawn by the site principal investigator or appropriate sub-investigator at any time, subjects who receive at least one dose of study product will be encouraged to remain in the study for follow-up safety assessments.

Every attempt will be made to follow all protocol defined safety follow-up (solicited adverse events) to resolution or stabilization.

Subjects who withdraw, or are withdrawn or terminated from the study, or discontinue treatment will not be replaced.

